### **11.2.4. Adverse Events Leading to Glucocorticoid Stress Dosing**

The number and percentage of subjects with a TEAE leading to glucocorticoid stress dosing will be presented by PT within SOC (presented in the same method as the analogous primary TEAE table) by treatment group. The first line of each table will display the number and percentage of subjects with at least one TEAE leading to glucocorticoid stress dosing. This summary will be produced for the DB period and OL period separately.

An overall summary table will be provided that summarizes the maximum severity of glucocorticoid stress dosing based on the following categories (in order of least to most severe):

- Oral dosing (alone, without parenteral dosing/ER visit/SAE)
- Parenteral dosing (without ER visit/SAE)
- ER visit without SAE (requiring glucocorticoid stress dosing)
- SAE (requiring glucocorticoid stress dosing)

Each subject will be counted once by their maximum severity of illness requiring glucocorticoid stress dosing. This table will be produced for the DB period and the OL period separately.

### **11.2.5. Exposure-Adjusted Subject Incidence Rate**

Exposure-adjusted subject incidence rate will be defined as the number of unique subjects experiencing the TEAE one or more times (numerator) divided by the sum of the time at risk for the first TEAE across all subjects (denominator). For subjects experiencing the TEAE, the time at risk (exposure time) is the time from the first dose to the date of the first occurrence of the TEAE. For subjects not experiencing the TEAE, exposure time is the time from the first dose to the last dose + 28 days (or data cutoff). Note that exposure time will vary across subjects for the

same TEAE. The exposure-adjusted subject incidence rate in the crinecerfont and placebo groups will be summarized by descending preferred term in the crinecerfont group.

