### 11.1. Study Drug Dosing and Compliance

The duration of exposure to crinecerfont will be calculated as: (last dose date – first dose date +1) regardless of when the exposure to crinecerfont began and ended (i.e., duration of exposure to crinecerfont will be an overall measure of exposure over the DB and OL periods and will not be presented separately for the DB and OL periods).

Duration of exposure will be summarized with descriptive statistics. The number and percentage of subjects with the following exposure categories will also be presented:

- > 0 to < 4 weeks
- $\geq$  4 weeks to < 24 weeks
- $\geq$  24 weeks to < 9 months
- $\geq$  9 months to < 12 months
- $\geq$  12 months

At each visit where study drug is dispensed, the site will enter the kit number(s) dispensed and returned as well as the total number of capsules dispensed and returned for the kits combined. The subject's compliance will be calculated at each visit (when kits are returned) as the total number of capsules dispensed – total capsules returned divided by the expected number of capsules taken by the subject during the visit interval. The number and percentage of subjects in each treatment group who are dosing compliant (defined as  $>120\%$ ,  $\geq 80\%$  to  $\leq 120\%$ , and  $<80\%$ ) will be presented for each postbaseline visit where study drug is returned. Compliance will be summarized separately for the DB and OL periods.

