### 11.2. Adverse Events

A treatment-emergent adverse event (TEAE) is an AE not present prior to the initiation of study drug dosing, or is an already present event that worsens either in intensity or frequency following the initiation of study drug dosing with an onset on or before the last dose of study drug + 28 days (to account for the study drug washout period).

TEAEs will be further defined for the two treatment periods. For the DB period, Investigators will be asked to respond “Yes” or “No” on the eCRF as to whether the AE started after the subject took the first dose of study drug. An AE with a response of “Yes” and that occurs on or before the last dose of study drug in the DB period will be classified as a TEAE for the DB period. If the subject’s last dose on study occurs in the DB period, then any AE occurring prior to the last dose of study drug in the DB period + 28 days will be considered a TEAE. If the investigator’s response is missing, then the treatment emergent status will be derived based on the AE onset date relative to the date of the subject’s first dose of study drug in the DB period or first dose of study drug in the OL period. If the AE onset date is unknown, it will be assumed that the AE is a TEAE and will be reported in the DB period TEAE summaries.

For the OL period, TEAEs will be defined as AEs starting after the first dose of study drug in the OL period and prior to the last dose of study drug in the OL period. If the subject’s last dose on study occurs in the OL period, then any AE occurring prior to the last dose of study drug in the OL period + 28 days will be considered a TEAE.

Adverse events with an onset date after the last dose of study drug + 28 days will not be considered treatment emergent (non-TEAEs).

The following TEAE summaries will be produced for the DB period (Day 1 up to Week 24) and for the 6-month OL period (Week 24 to Month 12) separately:

TEAEs categorized by MedDRA system organ class (SOC) and/or preferred term (PT) will be summarized in frequency tables. The frequency tables will include the number and percentage of unique subjects experiencing each event one or more times by treatment group.

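### Read as a double-blind table, the exposure-adjusted AE rate gives subjects who continue 28 days at risk in which no event can be counted, so absolute rates come out about 10–14% too low

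*SAP*

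**What the plan says.** SAP 11.2.5 divides the number of subjects with a given TEAE by the summed time at risk. For a subject with the event, "the time at risk (exposure time) is the time from the first dose to the date of the first occurrence of the TEAE". For a subject without it, "exposure time is the time from the first dose to the last dose + 28 days (or data cutoff". The section does not say which period's last dose is meant, does not define the cutoff, and makes no exception for subjects who move on to open-label treatment. On presentation it says: "The exposure-adjusted subject incidence rate in the crinecerfont and placebo groups will be summarized by descending preferred term in the crinecerfont group".

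SAP 11.2 starts from a general TEAE definition, "with an onset on or before the last dose of study drug + 28 days (to account for the study drug washout period", and then narrows it by period. For the double-blind period, an event reported as starting after the first dose "that occurs on or before the last dose of study drug in the DB period will be classified as a TEAE for the DB period". The 28-day tail is restored only for a subject whose last dose on study falls in the double-blind period: "then any AE occurring prior to the last dose of study drug in the DB period + 28 days will be considered a TEAE".

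Three other places bear on the reading:
- The introduction to SAP Section 11 makes double-blind and open-label safety summaries separate unless otherwise noted.
- SAP 6.1 uses crinecerfont and placebo as the double-blind group names. The open-label groups carry two-part names.
- Protocol Section 7 starts crinecerfont for all subjects on the evening of the Week 24 visit, so there is no washout.

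**The concern.** An exposure-adjusted rate is useful only if every day in the denominator is a day on which an event could have entered the numerator. For subjects who continue, that fails here: event counting stops at the last double-blind dose and the clock runs on. The surplus days carry no countable event, so the rate is diluted in both arms and always downward.

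For placebo subjects the surplus days are also spent on the test drug. The placebo column is then not purely a placebo rate, although it is labelled as one. Absolute rates are all that this table reports.

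**Working it through.** The SAP gives no numerical rate, person-time or worked example, so there is no figure to reproduce. The size follows from the definitions.

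**Inputs from the documents.** Double-blind treatment lasts 24 weeks = 168 days. The tail is 28 days. Months are 4 weeks, so Month 12 is Day 336. Planned placebo group: 55 subjects.

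**Assumptions, not in the documents.** Constant hazard; 24-week risk of a given AE between 1% and 50%; 90% to 100% of subjects continue into the open-label period.

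**Event-free subject who continues.** 168 + 28 = 196 days, and 168/196 = 0.857. For very rare events this is the fraction of the true rate that is reported.

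**General risk.** Let P be the 24-week risk, L = −ln(1 − P)/168 the daily hazard, D the surplus days and c the share continuing.
- Matched person-days per subject = P/L
- Person-days as written = P/L + (1 − P) × D × c
- Understatement = 1 − matched/as written

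Only event-free subjects receive the surplus, hence the factor (1 − P). With D = 28 and c = 1:

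| 24-week risk | Matched days | Days as written | Matched rate /100 PY | Rate as written | Understatement |
|---|---|---|---|---|---|
| 1% | 167.2 | 194.9 | 2.2 | 1.9 | 14.2% |
| 10% | 159.5 | 184.7 | 22.9 | 19.8 | 13.6% |
| 20% | 150.6 | 173.0 | 48.5 | 42.2 | 12.9% |
| 50% | 121.2 | 135.2 | 150.7 | 135.1 | 10.4% |

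With c = 0.9 the range is 9.4% (50% risk) to 13.0% (1% risk).

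**Placebo time on crinecerfont.** The surplus days are the open-label days, so their share of placebo person-time equals the understatement: about 10–14%. For 55 event-free placebo subjects, 55 × 168/365.25 = 25.3 person-years becomes 55 × 196/365.25 = 29.5.

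**Comparison between arms.** Assume true risks of 20% on crinecerfont and 10% on placebo.
- Rate ratio: 48.51/22.91 = 2.12 matched; 42.23/19.78 = 2.14 as written.
- Rate difference: 48.51 − 22.91 = 25.60 matched; 42.23 − 19.78 = 22.45 as written. This is 12.3% smaller.

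**Other readings of the same sentence.**
- *Last dose on study, taken to fall at Month 12 (an assumption).* 336 + 28 = 364 days, so D = 364 − 168 = 196. At 10% risk the rate is 10.9 instead of 22.9 per 100 PY, 52.5% too low. The range is 45–54% with all continuing and 42–51% with 90%. The 55 event-free placebo subjects would contribute 54.8 person-years. The rate ratio becomes 2.19.
- *General TEAE definition as numerator, last dose at Month 12.* The windows match and the understatement disappears. But placebo subjects kept in their randomized column then contribute open-label crinecerfont events and time. With the same 20% and 10% risks, the placebo rate rises from 22.9 to 35.5 per 100 PY, and a true ratio of 2.12 appears as 48.5/35.5, about 1.36 to 1.37 (1.36 unrounded).

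**The case against.** The best defence is that 11.2.5 can be read so that the windows agree. Its last dose + 28 days is the wording of the general TEAE definition that opens 11.2. Sections 11.2.1 to 11.2.4 each say that double-blind and open-label are produced separately, and 11.2.5 does not. This stands as a real ambiguity, so it would be wrong to say that no reading matches. It does not rescue the table, because under that reading the placebo column mixes in open-label crinecerfont events and time, and the between-arm ratio suffers more. The Section 11 default and the group names also point to a double-blind table.

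A second defence is that the cutoff in 11.2.5 could be the end of the double-blind period. Nothing says so, and SAP 5.2 has data through Month 12 analysed at the same time as the Week 24 results.

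The consequences are limited, and this also stands. Safety is descriptive with no hypothesis test. The main AE, SAE, discontinuation, adrenal insufficiency and stress-dosing tables use counts and percentages, not this denominator. Subjects with the event stop at its first occurrence. Subjects whose last dose on study is in the double-blind period have matching windows already.

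**Conclusion.** The concern holds in a conditional form. If the table is a double-blind one and the last dose is the last double-blind dose, the rule as worded yields a wrong rate; it does not merely lack detail. Absolute rates are about 10–14% too low with all subjects continuing and about 9–13% with 90%, under constant hazard and 24-week risks of 1% to 50%. Rate differences shrink with them (12.3% in the example).

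A reader might infer three stronger things that the documents do not support:

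- **That less than half of the true rate will be reported** (168/364 = 46%). SAP 11.1 does say that "duration of exposure to crinecerfont will be an overall measure of exposure over the DB and OL periods", but that is a measure of crinecerfont exposure only. 11.2.5 defines its own exposure time without referring to it, and a placebo denominator cannot be taken from it. The figure also needs the last dose to fall at Month 12, although dosing continues beyond that. It shows how wide the wording is, not what the plan prescribes.
- **That the comparison between arms is materially distorted.** With the double-blind numerator the ratio moves from 2.12 to 2.14. Unequal dropout adds little. Suppose, for rare events, that 20% of one arm stops at a mean of Day 84, with 84 + 28 = 112 matched days. That arm's inflation is (0.8 × 196 + 0.2 × 112)/(0.8 × 168 + 0.2 × 112) = 179.2/156.8 = 1.143, against 196/168 = 1.167 with no dropout, a shift of about 2%.
- **That the main safety tables or any efficacy conclusion are affected.** None uses this denominator.

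The point is worth settling before the table is programmed.

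**What to change.** In SAP 11.2.5, name the period and define the last dose and the data cutoff for it. For the double-blind rate, end the time at risk of an event-free subject where the TEAE window of 11.2 ends:

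- at the last double-blind dose for a subject who enters the open-label period;
- at the last double-blind dose + 28 days only for a subject whose last dose on study was in the double-blind period.

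Report open-label rates separately, with time starting at the first open-label dose and the same matching at the end. The 28-day tail should not be given to subjects who go on dosing past Month 12.

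This takes a few sentences and no new data. The downside is that reported absolute rates become somewhat less favourable: at 10% risk, 22.9 instead of 19.8 per 100 person-years.

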### **11.3. Clinical Laboratory Data**

The hematology, clinical chemistry, coagulation, thyroid stimulating hormone (TSH), free thyroxine (T4), and PRA data will be summarized with descriptive statistics by treatment group and visit. Both observed values and changes from baseline will be summarized for the DB period and OL period separately.

Shift tables will be presented for selected clinical laboratory variables based on the reference range-based categories of “Low,” “Normal,” or “High.” A clinical laboratory variable value will be assigned to one of these three categories according to the reference ranges provided by the central clinical laboratory.

Two shift tables will be presented within the double-blind treatment period: shifts from baseline to Week 4 and shifts from baseline to Week 24. Each shift table will have four rows and four columns, with rows reflecting the reference range category at baseline (or missing if applicable), and columns reflecting the reference range category at the specified postbaseline visit (or missing if applicable). A “Total” row and “Total” column will also be included. The number and percentage of subjects in each shift category will be displayed in the table; percentages will be based on the number of subjects included in the table. Two additional shift tables will be presented within the OL period: shifts from baseline to Month 12 and shifts from OL baseline (Week 24) to Month 12.

Shift tables will be presented for the following clinical laboratory variables:

- aspartate aminotransferase (AST),
- alanine aminotransferase (ALT),
- alkaline phosphatase (ALP),
- total bilirubin,
- creatine kinase,
- creatinine,
- white blood cell count,
- absolute neutrophil count,
- hemoglobin,
- platelet count,
- TSH,
- Free T4, and
- PRA.

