Crinecerfont was also well tolerated up to a repeated dose of 100 mg/day for 56 days in the Phase 2 study in 361 male and female subjects with MDD (DFI5687). The most frequently reported TEAEs (more than 5% in any crinecerfont group and higher than placebo) were headache, nausea, dry mouth, dizziness, somnolence, constipation, fatigue, and neutropenia. One death (completed suicide) occurred in the study (crinecerfont 100 mg group); this event occurred approximately 3 weeks after the subject's last dose of study drug. The percentage of subjects with suicidal ideation or behavior during treatment was similar between the 5 treatment groups. The percentages of treatment-emergent SAEs were similar among the 3 crinecerfont treatment groups (0.8% in each crinecerfont group) and the placebo group (1.7%), but slightly higher in the escitalopram 10 mg group (4.3%). Overall, approximately 10% of subjects discontinued due to TEAEs, most commonly neutropenia. The subjects receiving crinecerfont with the TEAE of neutropenia were asymptomatic, and these values recovered/resolved within 20 days of occurrence. Analyses of potentially clinically significant abnormalities for laboratory, vital signs, and ECG showed similar results between the 5 treatment groups.

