## LIST OF ABBREVIATIONS

Abbreviation	Term
17-OHP	17-hydroxyprogesterone
A4	Androstenedione
ACTH	Adrenocorticotropic hormone
AE	Adverse event
ANCOVA	Analysis of covariance
BID	Twice daily
BLQ	Below the lower limit of quantification
BMD	Bone mineral density
BMI	Body mass index
BPRS	Brief psychiatric rating scale
BSA	Body surface area
CAH	Congenital adrenal hyperplasia
CI	Confidence interval
CMH	Cochran-Mantel-Haenszel
COVID-19	Coronavirus disease of 2019
CP	Conditional power
CSR	Clinical study report
C-SSRS	Columbia-Suicide Severity Rating Scale
CTx	Serum C-terminal telopeptide
DB	Double-blind
DMC	Data Monitoring Committee
DXA	Dual-energy X-ray absorptiometry
ECG	Electrocardiogram
eCRF	Electronic case report form
EMA	European Medicines Agency
EQ-5D-5L	EuroQol 5-Dimensions 5-Levels
EQ-VAS	EuroQol visual analog scale
FAS	Full analysis set
FCS	Fully conditional specifications
FDA	Food and Drug Administration
FSH	Follicle stimulating hormone

Abbreviation	Term
GC	Glucocorticoid
GFI	Global fatigue index
GTT	Glucose tolerance test
HbA1c	glycated hemoglobin
HDL	High-density lipoprotein
HOMA-IR	Homeostatic model assessment of insulin resistance
ICH	International Council for Harmonization
IPD	Important protocol deviation
IRT	Interactive response technology
ISC	Independent statistical center
IUD	Intrauterine device
LDL	Low-density lipoprotein
LH	Luteinizing hormone
LLN	Lower limit of normal
LS	Least squares
MAF	Multidimensional assessment of fatigue
MedDRA	Medical Dictionary for Regulatory Activities
MI	Multiple imputation
MOS-12	Medical outcomes study 12-item sleep scale
NBI	Neurocrine Biosciences, Inc.
NTx	urine N-terminal telopeptide
OL	Open-label
OLE	Open-label extension
PCS	Potentially clinically significant
PDHP	Protocol Deviation Handling Plan
PGWBI	Psychological general well-being index
PKAS	PK analysis set
PRA	Plasma renin activity
PT	Preferred Term
qAM	Every morning
QD	Once per day
QID	Four times per day

Abbreviation	Term
qPM	Every evening
SAE	Serious adverse event
SAP	Statistical analysis plan
SAS	Safety analysis set
SD	Standard deviation
SE	Standard error
SEM	Standard error of the mean
SF-36	36-Item Short Form Heath Survey
SHGB	Sex hormone binding globulin
SMQ	Standardized MedDRA Queries
SOC	System organ class
TART	Testicular adrenal rest tumor
TEAE	Treatment-emergent adverse event
TID	Three times per day
ULN	Upper limit of normal
ULQ	Upper limit of quantification
VAS	Visual analog scale
WHO	World Health Organization

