## 6.7. Study Day

For each subject, study day is calculated relative to Day 1, where Day 1 is defined as the date of first dose of study drug. If the date of interest occurs on or after Day 1, then the study day will be calculated as: date of interest – date of Day 1 + 1. If the date of interest occurs prior to Day 1, then the study day will be calculated as: date of interest – date of Day 1. For subjects who are randomized but never dosed, Day 1 will be defined as the subject's randomization date.

The nominal visit number for each visit, including scheduled, unscheduled, repeat, and early termination/end of study visits, will be re-mapped to an analysis visit according to [Table 4](#), [Table 5](#), [Table 6](#), [Table 7](#), [Table 8](#). If multiple measurements occur within the same visit window after mapping, the measurement that is closest to the target study day will be used for the summary tables where one observation per visit is needed, unless otherwise specified. Where there are ties between the earlier and later observation within the visit window, the earlier observation will be used. For the purpose of this study, months are defined as 4-week intervals.

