**Table 4: Primary Analysis Visit Windows**

Scheduled Visit	Target Study Day	Analysis Window (Study Day Range)
Week 2	14	2 to 21
Week 4	28	22 to 36
Week 6	42	37 to 53
Week 9	63	54 to 74
Week 12	84	75 to 98
Week 16	112	99 to 126
Week 20	140	127 to 154
Week 24	168	155 to (first dose date in OL period)
Month 7	196	(First dose date in OL +1) to 210
Month 8	224	211 to 238
Month 9	252	239 to 266
Month 10	280	267 to 308
Month 12	336	309 to (first dose date in OL/DB period)

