## 11.5. Electrocardiogram

Descriptive statistics for the observed values and changes from baseline will be presented for each of the ECG parameters (heart rate, PR interval, QRS duration, QT interval, QTcF) by visit and treatment group.

Frequency tables (number and percentage of subjects) will be presented for the investigator overall categorical assessment (ie, Normal, Abnormal not Clinically Significant, or Abnormal Clinically Significant) by visit and treatment group.

Two additional categorical summaries (frequency tables displaying number and percentage of subjects) will be presented for the QTcF interval by treatment group. For the first summary, the observed QTcF values at each visit will be classified as follows:

- Greater than 450 msec
- Greater than 480 msec
- Greater than 500 msec

For the second categorical summary, the changes from baseline to each subsequent visit will be classified as follows:

- Increase greater than 30 msec
- Increase greater than 60 msec

The same categorical summaries will be presented in frequency tables for values at any postbaseline visit (including unscheduled and early termination visits) meeting the aforementioned criteria.

The above ECG summaries will be produced for the DB period and the OL period separately.

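### SAP 11.3 counts subjects with ALT, AST, ALP or bilirubin above ULN at only 3 of 11 postbaseline chemistry visits to Month 12, and plans no count above multiples of ULN, at any visit, or for ALT/AST with bilirubin

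*SAP*

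**What the plan says.** SAP 11.3 plans two kinds of output for the liver tests.

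- **By-visit descriptive statistics** by treatment group, for observed values and changes from baseline. Under SAP 6.1 these include n, mean, median, minimum and maximum. SAP 11 adds a safety follow-up visit to all by-visit safety tables.
- **Shift tables** by Low, Normal or High for 13 analytes, among them AST, ALT, ALP and total bilirubin. Each value "will be assigned to one of these three categories according to the reference ranges provided by the central clinical laboratory". For timing: "Two shift tables will be presented within the double-blind treatment period: shifts from baseline to Week 4 and shifts from baseline to Week 24". The open-label period has two more, from baseline and from the open-label baseline, both to Month 12.

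Where several values fall in one visit window, SAP 6.7 says that "the measurement that is closest to the target study day will be used for the summary tables where one observation per visit is needed".

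For QTcF, SAP 11.5 goes further. It counts subjects above graded thresholds, with "frequency tables for values at any postbaseline visit (including unscheduled and early termination visits".

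The SAP abbreviation list defines PCS as "Potentially clinically significant", but no section of the text supplied uses it. Of the Phase 2 depression study, which dosed "up to a repeated dose of 100 mg/day for 56 days", Protocol 5.2 reports: "Analyses of potentially clinically significant abnormalities for laboratory, vital signs, and ECG showed similar results between the 5 treatment groups".

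Protocol 13.6.2 asks only for descriptive statistics on selected laboratory analytes.

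**The concern.** A reader of the study report will want three facts about liver tests in each arm: how many subjects had a clearly raised value, how high it went, and whether raised transaminases and raised bilirubin occurred in the same person. The planned laboratory tables answer these only in part. The High column does not separate a value just above ULN from one many times ULN. Exclusion criterion 9 admits ALT and AST up to 3 x ULN, so some subjects may start in that column. Each analyte is tabulated alone, so no table links ALT/AST with bilirubin.

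Liver is a reasonable place to ask for more. Protocol 5.2 lists it among the main target organs in mouse, rat and dog. The dose in this trial is not new to humans, but the duration is. If one by-visit maximum is high, the report cannot say from the laboratory tables how many subjects lie behind it.

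**Working it through.** The plan states no figure on this point, so there is none to reproduce. The check is a count of visits, followed by what can and cannot be recovered from the planned tables.

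**Step 1. Scheduled postbaseline chemistry visits within this SAP (Day 1 to Month 12).**
- Double-blind (Protocol Table 1): Weeks 4, 6, 9, 12, 16, 20, 24 = 7.
- Open-label (Protocol 9.7.3.2, 9.7.3.3 and 9.7.4.1): Months 8, 9, 10, 12 = 4. Month 7 has hematology and coagulation but no chemistry.
- Total: 7 + 4 = 11.

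**Step 2. Visits with a count above ULN.**

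| Period | Chemistry visits | With a shift table | Without |
|---|---|---|---|
| Double-blind | 7 | 2 (Weeks 4, 24) | 5 (Weeks 6, 9, 12, 16, 20) |
| Open-label | 4 | 1 (Month 12) | 3 (Months 8, 9, 10) |
| Both | 11 | 3 (3/11 = 27%) | 8 (8/11 = 73%) |

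All 8 visits without a shift table still have by-visit statistics, including the maximum.

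**Step 3. What the maxima can show.** If every by-visit maximum is below a threshold, the count above it is zero for the values kept. Once a maximum exceeds it, the number of subjects is unknown. Illustration with assumed levels: the ALT maximum in the crinecerfont arm (110 planned) exceeds 3 x ULN at each of the 5 visits from Week 6 to Week 20. This fits one subject with a sustained rise, 1/110 = 0.9%, or five different subjects, 5/110 = 4.5%, or more.

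**Step 4. Which values are kept.** The Week 16 window in SAP Table 4 is Days 99 to 126, with target Day 112. Assume a scheduled draw on Day 107 at 6 x ULN and a repeat on Day 110 at 2 x ULN. The distances are |107 - 112| = 5 and |110 - 112| = 2. The repeat is kept and the peak is absent from that by-visit table.

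**Step 5. Prior exposure.** Protocol 5.2 and 5.3 describe up to 400 mg/day for 16 days, 300 mg/day for 28 days and 100 mg/day for 56 days. The longest course at 200 mg/day or more is therefore 28 days. This SAP covers 200 mg/day for 168 days, and up to 336 days in the crinecerfont arm: 168/28 = 6 and 336/28 = 12 times as long.

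**Step 6. After the fix.** An any-visit count covers 11 of 11 scheduled chemistry visits, plus unscheduled and early termination values.

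**The case against.** The case against is substantial.

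- **No requirement is breached.** SAP 11.3 delivers what Protocol 13.6.2 asks for. This stands, and it sets the weight of the point.
- **No signal is known.** Protocol 5.2 puts the no-effect exposures at or above the maximum expected human exposure, Protocol 9.6.1 states no identified risks, and the earlier human studies report no liver laboratory concern. This stands too.
- **Adverse events give subject counts.** SAP 11.2 counts unique subjects by preferred term and 11.2.5 adds exposure-adjusted incidence. This helps only for values that an investigator reports as an adverse event. Medical Monitor and DMC review protect subjects but put no count by arm in the report.
- **The counts could be run later.** They could, but SAP 6.1 would label them post hoc.
- **The thresholds are not the trial's own.** Only 3 x ULN appears in the protocol, as an entry limit; the entry limit for bilirubin is 1.5 x ULN. This stands, so the cut-offs below are examples and the sponsor's own criteria come first.
- **The comparisons are loose.** QTcF has a stopping rule and liver tests have none. An unused abbreviation shows nothing about intent, and the sentence on the depression study does not mention liver tests. SAP 11.5 shows only that the sponsor already uses this kind of table.

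A reader might go further and infer that subjects who leave mid-period vanish from the laboratory reporting. The documents do not support that. Such a subject is in the Week 4 shift table if sampled then, in the by-visit tables for visits attended, and, after stopping both drug and study, in the safety follow-up summary if sampled within its window (SAP 11 and Table 5). Subjects who stop only study drug are to stay under assessment to Month 18 (Protocol 9.10). Nor do the intervals between shift tables amount to unreported time, because every chemistry visit within them has by-visit statistics.

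**Conclusion.** The point holds as an optional, low-cost improvement. Subjects above ULN are counted at 3 of 11 scheduled chemistry visits. Three summaries are absent from the SAP text supplied: counts above multiples of ULN, counts at any postbaseline visit, and a joint count of ALT/AST with bilirubin. The planned by-visit tables cannot stand in for them, because a maximum gives neither the number of subjects nor a link between analytes, and the one-value-per-window rule can drop a peak.

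The visit count rests on the scheduled visits to Month 12; SAP section 1 leaves the period from Month 12 to Month 18 to an amendment. The 0.9% versus 4.5% contrast and the dropped-peak example use assumed laboratory values and assume that the abnormal values are not each reported as adverse events. The documents do not say how many subjects will enter above ULN. Nothing here shows a conflict between the SAP and the protocol, or a known liver risk.

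**What to change.** In SAP 11.3, for the double-blind and open-label periods separately and by treatment group, add a table of how many subjects (n, %) have at least one postbaseline value in the period meeting each of these:

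- ALT or AST above graded multiples of ULN, for example >3, >5 and >10 x ULN;
- total bilirubin >2 x ULN;
- ALT or AST >3 x ULN together with bilirubin >2 x ULN, in the same sample or within a window fixed in advance.

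If the sponsor has standard PCS criteria, use those instead.

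State the rules with the table:

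- Include unscheduled, early termination and safety follow-up values, up to last dose + 28 days when the last dose falls in that period. This matches the TEAE limit in SAP 11.2. The final visit is due at 28 days with a window of +7 days (+14 for subjects who entered the extension), so say how samples drawn after day 28 are treated.
- Split each row by Day 1 status, at or below ULN versus above ULN, in both periods. The open-label baseline is already on treatment for the crinecerfont arm.
- Flag documented Gilbert's syndrome, which exclusion criterion 9 exempts from the bilirubin limit.
- List every subject who meets the combined criterion.

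The cost is SAP wording, one or two descriptive tables and a short listing. No new sample or visit is needed, and the efficacy analyses and type I error are untouched. The downside is small counts to interpret without formal testing.
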